organs, Cohort 2 (300 µg; 7.4 GBq/cycle; cumulative 22.2 GBq; [Table 2](#)) will be initiated (see priority classification in [Figure 2](#)). However, if improved safety regarding DLTs is seen with increased peptide mass, Cohort 2 (300 µg; 7.4 GBq/cycle; cumulative 22.2 GBq) may be delayed until experience is gained with the 7.4 GBq dose at the higher peptide mass (700 µg). If optimal peptide mass is evaluated to be >300 µg then this cohort will not be opened.

Intra-individual peptide mass dose evaluation (Cohorts 3 and 6 – Part B)

Cohorts 3 and 6 will allow the intra-individual evaluation of peptide mass. In both Cohorts 3 and 6, subjects will receive the same cumulative radioactivity as in Part A (4.5 GBq/cycle; cumulative, 13.5 GBq; [Table 2](#)). The associated peptide mass dose will also be the same (300 µg) in Cycles 1 and 3, and will be increased to 700 µg in Cohort 3 and 1300 µg in Cohort 6 during Cycle 2.

Peptide mass dose escalation (Cohorts 4 and 5 and optional Cohorts 7 and 8 – Part B)

In Cohort 4, subjects will receive 6 GBq/cycle (cumulative 18 GBq) with a peptide mass dose of 700 µg, for three cycles ([Table 2](#)). After one cycle, if no safety signal is observed in Cohort 4, Cohort 5 will be initiated. In Cohort 5, subjects will receive 7.4 GBq/cycle (cumulative, 22.2 GBq) with a peptide mass dose of 700 µg, for three cycles ([Table 2](#)).

Cohorts 7 and 8 will be cancelled if ssr2 saturation is seen with peptide mass dose of 700µg and 1300 µg in Cohort 3 or 6 and/or if there are other safety signals ([Table 2](#)). There will be no further dose escalation of OPS201 peptide after 1300 µg.

The dose escalation rules

The DRB will consist of a team of “permanent” decision makers (the core team), including selected principal investigators and Ipsen personnel. All final decisions will be made by the core team. The number of DRB meetings may change as needed and the DRB can be called upon rapidly if there is a safety issue of concern in a cohort. The aim is to have all meetings via conference call, but if the timing does not allow for this, then the meeting can be conducted via email exchange or two conference calls with split attendees. A DRB charter will be developed with further details. Ad-hoc DRBs can be convened at any time during the trial.

Dose escalation (peptide mass dose and radioactivity, see [Figure 2](#)) will primarily be decided based on the clinical and safety data of the subjects.

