2.3 Study Hypotheses

- (1) ^{177}Lu -OPS201 will be sufficiently safe to permit further clinical investigation when administered in previously treated subjects with unresectable GEP NETs, lung NETs and malignant, unresectable pheochromocytoma or paraganglioma.
- (2) Increase of peptide mass doses leads to improved tumour to background ratio for ^{177}Lu -OPS201 administration, with a possible positive impact on the safety profile with an increasing tumour to bone marrow ratio.

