The DRB will consist of a team of “permanent” decision makers (the core team), including selected principal investigators and Ipsen personnel. All final decisions will be made by the core team. The number of DRB meetings may change as needed and the DRB can be called upon rapidly if there is a safety issue of concern in a cohort. The aim is to have all meetings via conference call, but if the timing does not allow for this, then the meeting can be conducted via email exchange or two conference calls with split attendees. A DRB charter will be developed with further details. Ad hoc DRBs can be convened at any time during the trial. See [Appendix 3](#) for the details of the review required by the DRB.

Dose escalation (peptide mass dose and radioactivity, see [Figure 13](#)) will primarily be decided based on the clinical and safety data of the subjects.

Dose limiting toxicity (DLT) definition in Part B: IRPP related AEs with a severity of Grade 3 or higher are considered DLTs, with the exception of hair loss, lymphopenia, nonfebrile neutropenia lasting <4 weeks and thrombocytopenia lasting <4 weeks.

Proceeding to the next cohort will be determined by the following DLT rules based on three evaluable subjects:

If DLTs occur in $> 33\%$ of subjects in the cohort, the next cohort will not be initiated.

- If DLTs occur in $\leq 33\%$ and ≥ 2 of the three subjects have a cumulative absorbed dose in each target organ exceeding the acceptability limits (1.5 Gy in BM and 23 Gy in kidney), subjects in the next cohort will receive the same cumulative radioactivity or less than in the preceding cohort.
- If DLTs occur in $\leq 33\%$, and < 2 of the three subjects did not reach the cumulative absorbed dose in each target organ (1.5 Gy in BM and 23 Gy in kidney), the next cohort will be initiated as planned.

Each dose escalation (both peptide mass and radioactivity) will be carefully evaluated by the DRB. As safety and dosimetry information becomes available in other cohorts, this data will be used to evaluate the on-going cohorts and the subjects’ dosing within the cohorts.

The DRB can make a recommendation as to the radioactivity dosing for the next cohort. This could include continuing the current cohort to complete five subjects for review. Alternatively, if any cohort dose (peptide or radioactivity) is closed down, with agreement from the DRB, the

next lowest dose may have three more subjects entered to confirm this is the maximum tolerated dose.

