3.2.18 Role of the Safety Review Committee (SRC) – Part A

The SRC will be composed of all Investigators, who have treated at least one subject in the study with study medication, a dosimetry expert evaluating the dosimetry data of the study, an independent hematology expert and at least one Sponsor representative. A specific charter will be developed to define roles and responsibilities, as well as the data set to be reviewed by the SRC.

This study will be performed in two parts:

Part A (15 subjects)

Initially, 6 subjects will be treated. Each patient will receive:

- 3 cycles of 4.5 GBq (target radioactivity of 4.5 GBq±10%) ¹⁷⁷Lu-OPS201 (target dose of 300±50 µg), 8 weeks apart (+2 weeks or plus up to 4 weeks in case of AEs which have not adequately recovered).

A SRC meeting will be held before exposing the remaining 9 subjects of Part A to the entire number of planned administrations. Safety and dosimetry data from the first 6 subjects (data obtained up to 8 weeks after the last administration for each subject) will be evaluated during this SRC.

Dose limiting toxicity (DLT) definition: Investigational medicinal product (IRPP) related AEs with a severity of Grade 3 or higher are considered DLT, with the exception of hair loss, lymphopenia, nonfebrile neutropenia lasting < 4 weeks and thrombocytopenia lasting < 4 weeks.

- If DLTs occur in ≤ 33% of the patients (i.e. ≤ 2 of 6 patients), the remaining 9 patients will continue at the same radioactivity level.

- If DLTs occur in > 33% of the patients (i.e. > 2 of 6 patients), the administered radioactivity will be reduced to a cumulative radioactivity which did not lead to DLT occurrence with this frequency, e.g. the number of administrations will be reduced from 3 to 2.

Part B (up to 40 subjects)

Proceeding to next cohort will be determined by the following DLT rules based on three evaluable subjects:

- If DLTs occur in >33% of the subjects of the cohort, the next cohort will not be initiated.
- If DLTs occur in $\leq 33\%$ and ≥ 2 of the three subjects have cumulative absorbed dose in each target organs exceeding the acceptability limits (1.5 Gy in bone marrow (BM) and 23 Gy in kidney), subjects in the next cohort will receive the same cumulative radioactivity or less than in the preceding cohort.

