DRB-B	Cohort 3 First three subjects, EOC-2	Start Cohort 4 with 6 GBq?	If >65% DLTs in Cohort 3 then NO to Cohort 4. If >33% and <67% DLTs in Cohort 3 Cycle 2 then wait for three more subjects in Cohort 3 Cycle 2 and re-evaluate. Otherwise start Cohort 4. Cohort 4 will not start recruiting until Cohorts 1, 3 and 6 are fully recruited
DRB-C	Cohort 4 EOC-1	Start Cohort 5? Continue Cohort 4?	If >33% DLTs in Cohort 4 then NO to Cohort 5. If >33% DLTs in Cohort 4 then STOP. Evaluate peptide mass dosing and lesion receptor saturation. Evaluate next cohort to start and activity dosing.
DRB-D	Cohort 6 EOC-3 All subjects Cohort 4 EOC-1	Start Cohort 7?	If >33% DLT in Cohort 6 Cycle 2 NO to Cohort 7 AND If lesion receptor saturation in Cohort 6 Cycle 2, then no to Cohort 7 AND If >33% DLTs and <67% DLTs in Cohort 4 and receptor modelling suggests Cohort 7 mass dose safer, then start Cohort 7, otherwise no.
DRB-E	Cohort 6 EOC-3 All subjects Cohort 5 EOC-1	Start Cohort 8?	If >33% DLT in Cohort 6 Cycle 2 NO to Cohort 8 AND If lesion receptor saturation in Cohort 6 Cycle 2, then no to Cohort 8 AND If >33% DLTs <67% DLTs in Cohort 5 and receptor modelling suggests Cohort 8 mass dose safer, then start Cohort 8, otherwise no.
DRB-F	Cohort 1 EOC-3 and Cohort 3 EOC-3 and Cohort 5 EOC-1	Start Cohort 2?	If mass dose modelling suggest 300 ug is optimal AND If >33% DLTs in Cohort 1, AND If >33% DLTs in Cohort 5 Start Cohort 2

DLT=dose limiting toxicity; DRB=data review board; EOC=end of cycle; GBq=gigabecquerel.

Note: At each DRB, safety data available from all cohorts will be evaluated to inform decision making.

a although the DRBs are written in alphabetical sequence this is not a chronological order; each one will be conducted when data becomes available which is dependent on subject recruitment. An ad-hoc DRB can be called to ensure continuity of dosing. Although three completed subjects are required for each completed cycle for evaluation, all available subject data in that cohort will be used (e.g. If five subjects are enrolled and all five complete the end of a cycle prior to the DRB, then all five sets of data will be evaluated).

This cumulative activity in the cohort being evaluated will be determined by the following DLT rules:

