- If, in the preceding cohort after the third administration of ¹⁷⁷Lu-OPS201, DLTs occur in >33% of three subjects (i.e. >1 out of the three to five subjects), the activity for the next cohort will be reduced to a cumulative administered activity which did not lead to DLT occurrence with this frequency.
- If, in the preceding cohort after the third administration of 6GBq ¹⁷⁷Lu-OPS201, DLTs occur in ≤33% of three subjects and ≥2 of the three subjects have a cumulative absorbed

dose in each target organ exceeding the acceptability limits (1.5 Gy in BM and 23 Gy in kidney), subjects in the next cohort will receive the same cumulative activity or less than in the preceding cohort.

- If, in the preceding cohort after the third administration of 6GBq ¹⁷⁷Lu-OPS201, DLTs occur in ≤33% of the three subjects and less than two of the three subjects did not reach the cumulative absorbed dose in each target organ (1.5 Gy in BM and 23 Gy in kidney), the activity in the next cohort will be escalated up to 7.4 GBq per administration, as detailed in the table above

Data Review Board

- the DRB will consist of a team of “permanent” decision makers (the core team);
- principal investigators may participate, present and listen in;
- all final decisions will be made by the core team;
- the number of DRB meetings may change as needed and can be called upon rapidly if there is a safety issue of concern in a cohort;
- the aim is to have all meetings via conference call, but if the timing does not allow for this, then it can be conducted via email exchange or two conference calls with split attendees;
- a DRB charter will be developed with further details.

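### SAP Table 9 can open Cohort 7 or 8 after more than 33% DLTs in Cohort 4 or 5, without reconciling this with the general bar, requiring lower activity, or using the protocol's saturation trigger

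*SAP*

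**What the plan says.** SAP 3.2.19, Table 9, sets out what each planned Data Review Board (DRB) meeting decides. DRB-D decides on Cohort 7 (1300 µg, 6.0 GBq) from all Cohort 6 subjects at the end of Cycle 3 and from Cohort 4 (700 µg, 6.0 GBq) at the end of Cycle 1. Its last condition is: "If >33% DLTs and <67% DLTs in Cohort 4 and receptor modelling suggests Cohort 7 mass dose safer, then start Cohort 7, otherwise no". DRB-E decides on Cohort 8 (1300 µg, 7.4 GBq) from Cohort 6 and from Cohort 5 (700 µg, 7.4 GBq): "If >33% DLTs <67% DLTs in Cohort 5 and receptor modelling suggests Cohort 8 mass dose safer, then start Cohort 8, otherwise no". Both rows refuse the new cohort if Cohort 6 Cycle 2 shows more than 33% DLTs or lesion receptor saturation.

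The general Part B rule, in SAP 3.2.18, is: "If DLTs occur in >33% of the subjects of the cohort, the next cohort will not be initiated". Protocol 3.8 says the same. Neither states an exception.

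SAP 3.2.19 gives another response when DLTs exceed 33% after the third administration in the preceding cohort: "the activity for the next cohort will be reduced to a cumulative administered activity which did not lead to DLT occurrence with this frequency". At DRB-C, more than 33% DLTs in Cohort 4 means no Cohort 5 and a stop, followed by a review that includes: "Evaluate next cohort to start and activity dosing".

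On saturation, protocol 3.1.3 cancels Cohorts 7 and 8 if it is seen in Cohorts 3 and/or 6. The protocol synopsis names Cohort 3 or 6.

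**The concern.** The decision concerns safety: whether to give 1300 µg at an activity that has just produced DLTs in, for example, 2 of 3 subjects at 700 µg. A board applying the general rule could conclude that it must not open the cohort. A board applying Table 9 could conclude that it should. The plan does not say which governs.

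If the board follows Table 9, the SAP's only compulsory activity reduction is tied to a later time point than the data in hand, so any reduction is left to the board's judgement. On saturation, a finding in Cohort 3 alone would cancel Cohorts 7 and 8 under the protocol but would not stop them under Table 9.

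Cohorts 3 and 6 address peptide mass in any case. What is affected is whether, and at what activity, 1300 µg is studied at the higher radioactivity levels.

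**Working it through.** **Inputs.** The bar is above 33% (SAP 3.2.18, protocol 3.8), based on three evaluable subjects. The start band is above 33% and below 67% (SAP Table 9). These cohorts enrol three to five subjects (protocol 3.1.2). Protocol 3.1.3 plans three in each remaining cohort if all are used: 10 + 10 + 5 = 25 in Cohorts 3, 6 and 1, plus 5 × 3 = 15, total 40.

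**The plan's own figure.** SAP 3.2.19 glosses above 33% as more than 1 of three to five subjects. Reading 33% as one third reproduces this: 1/3 does not exceed it, while 2/3 (66.7%), 2/4 (50%) and 2/5 (40%) do.

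**Counts in each region.**

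| Subjects | Not barred | Barred, but in the Table 9 start band | Barred, and no under Table 9 |
|---|---|---|---|
| 3 | 0, 1 | 2 | 3 |
| 4 | 0, 1 | 2 | 3, 4 |
| 5 | 0, 1 | 2, 3 | 4, 5 |

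The middle column can be reached at every planned size.

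**Probability of the middle column.** P = Σ C(n,k) pᵏ(1−p)ⁿ⁻ᵏ over the counts shown. For n = 3 this is 3p²(1−p); at p = 0.30 it is 3 × 0.09 × 0.70 = 0.189. The documents give no DLT risk, so p is an assumption and a range is shown.

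| Assumed DLT risk | 10% | 20% | 30% | 40% | 50% | 60% |
|---|---|---|---|---|---|---|
| 3 subjects | 2.7% | 9.6% | 18.9% | 28.8% | 37.5% | 43.2% |
| 4 subjects | 4.9% | 15.4% | 26.5% | 34.6% | 37.5% | 34.6% |
| 5 subjects | 8.1% | 25.6% | 44.1% | 57.6% | 62.5% | 57.6% |

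These figures cover the DLT count alone. The path also needs favourable modelling, no more than 33% DLTs in Cohort 6 Cycle 2 and no saturation there, so they are upper bounds. The evidence at that point is thin: the exact (Clopper-Pearson) 95% interval for 2 of 3 is 9% to 99%.

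**Activity.** In SAP Table 1, Cohort 7 has the same nominal activity as Cohort 4 (6.0 GBq per cycle, 18.0 GBq over three cycles). Cohort 8 has the same as Cohort 5 (7.4 and 22.2 GBq). The reduction rule operates after the third administration; DRB-D and DRB-E use Cohort 4 or 5 data from the end of Cycle 1. On those data the rule does not bind.

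**Saturation.** Suppose Cohort 3 shows saturation at 700 µg and Cohort 6 does not at 1300 µg. The cohorts enrol different subjects, and protocol 3.1.3 says saturation depends on tumour burden and receptor density, so this cannot be ruled out. Protocol 3.1.3 then cancels Cohorts 7 and 8; the Table 9 saturation condition does not.

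**The case against.** The strongest reply is that there is no contradiction. The bar applies to the *next cohort*, a term left undefined in a branched scheme. The protocol synopsis gives Cohort 4's successor: "After one cycle, if no safety signal is observed in Cohort 4, Cohort 5 will be initiated". On that reading Table 9 obeys the bar, since DRB-C refuses Cohort 5 above 33% DLTs. Table 9 can also be read as the specific rule: SAP 3.2.19 points to it for the decision details, and protocol 3.8 refers to Appendix 3. A rescue path has a rationale too, because the second hypothesis in protocol 2.3 expects more peptide to improve the tumour-to-background ratio "with a possible positive impact on the safety profile".

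This argument stands as far as it goes. A reader might infer that the SAP flatly permits what it forbids; the documents do not establish that. But no supplied sentence gives Table 9 precedence, and SAP section 5 lists no such departure from the protocol. DRB-C itself uses the term for whatever cohort opens after Cohort 5 has been refused. The ambiguity remains.

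A reader might also infer that activity is uncontrolled. It is not. DRB-C calls for a review of activity, protocol 3.8 lets the DRB recommend activity for the next cohort, and protocol 6.2 and 6.4.2 provide per-subject reduction and the 1.5 Gy and 23 Gy limits. What is missing is a reduction that binds at this decision.

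Finally, the closing words of each row also refuse Cohorts 7 and 8 after 0 or 1 DLTs. That might look like a second conflict with SAP 3.2.18. It is better seen as unexplained intent, since the successor to Cohort 4 named in the synopsis is Cohort 5.

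On saturation, the second interim analysis follows completion of Cohorts 3 and 6 and confirms whether Cohorts 7 and 8 open, so Cohort 3 data will be available. This narrows the practical gap but leaves the two triggers different.

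**Conclusion.** The point holds as two gaps in safety decision rules, not as a proven contradiction.

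First, at 2/3, 2/4, 2/5 or 3/5 DLTs in Cohort 4 or 5, Table 9 can start Cohort 7 or 8. The supplied text does not say how this fits with the general bar, and no mandatory activity reduction applies on end-of-Cycle-1 data. Second, the saturation trigger in Table 9 is narrower than the protocol's.

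Three subjects is the relevant size if all remaining cohorts are used. The chance of 2 of 3 DLTs is then 3% to 19% at assumed risks of 10% to 30%. The larger figures for four or five subjects, or for higher risks, should not be read as the chance that Cohort 7 or 8 opens this way, because the modelling and Cohort 6 conditions must also be met.

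Confidence is moderate. The conclusion rests on reading 33% as one third, as the SAP's own gloss implies, and on the supplied text: protocol Appendix 3, including Table 12, and the DRB charter were not available and may settle the precedence. Cohorts 7 and 8 are optional, which limits the practical weight.

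**What to change.** 1. In Table 9, change the DRB-D and DRB-E saturation condition to Cohorts 3 and/or 6, matching protocol 3.1.3. This is a wording change.
2. Decide whether the rescue path is intended.
   - If it is, write it as an explicit exception in SAP 3.2.18 and protocol 3.8. Require a stated, reduced activity for the rescue cohort based on end-of-Cycle-1 DLTs. Say whether Cohorts 7 and 8 may also open at 33% or fewer DLTs.
   - If it is not, gate DRB-D and DRB-E at 33% or fewer DLTs in Cohort 4 or 5, with the existing organ-dose conditions. This is a dose-escalation decision for the sponsor and DRB, not wording only.
3. Check protocol Appendix 3, Table 12, for the same text and amend it to match. While Table 9 is open, check the DRB-F row, which also uses more than 33% DLTs as a condition for starting a cohort.

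The cost is an SAP revision and a protocol amendment, plus the choice of an activity level if the rescue path is kept. No new data are needed, and no subjects beyond the Part B maximum of 40.

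### SAP Table 9: the DRB-F rule opens the 7.4 GBq Cohort 2 when Cohort 1 is too toxic, DRB-B gives two actions for 2 of 3 DLTs, and DRB-A answers for the wrong cohort

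*SAP*

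**What the plan says.** Section 3.2.19 of the SAP defines six DRBs in advance (A to F) and gives the decision rule for each in Table 9.

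- **DRB-F** decides whether to start optional Cohort 2. It uses Cohort 1 and Cohort 3 at the end of cycle 3 and Cohort 5 at the end of cycle 1. The first condition is "If mass dose modelling suggest 300 ug is optimal". The rest reads "If >33% DLTs in Cohort 1, AND If >33% DLTs in Cohort 5 Start Cohort 2".
- **DRB-B** decides on Cohort 4 from the first three Cohort 3 subjects at the end of cycle 2. Above 65% DLTs in Cohort 3 the answer is NO. Above 33% and below 67% in Cohort 3 Cycle 2, the board waits for three more subjects. Otherwise Cohort 4 starts.
- **DRB-A** uses the same Cohort 3 data. It asks whether Cohort 6 may start its second cycle at 1,300 µg. Its one criterion (above 33% in Cohort 3 Cycle 2) leads to NO for Cohort 4.

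The text after the table covers the step from 6 to 7.4 GBq. If DLTs exceed 33% after the third administration, the stated action is that "the activity for the next cohort will be reduced to a cumulative administered activity which did not lead to DLT occurrence with this frequency". The SAP explains that threshold as a count: ">1 out of the three to five subjects". A separate clause governs escalation. Its condition is that "DLTs occur in ≤33% of the three subjects and less than two of the three subjects did not reach the cumulative absorbed dose". Its action, once that condition is met, is that "the activity in the next cohort will be escalated up to 7.4 GBq per administration".

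SAP 3.2.18 gives the general Part B rule: with DLTs in more than 33% "of the subjects of the cohort, the next cohort will not be initiated". Protocol 3.8 says the same. The Protocol synopsis (radioactivity escalation, Cohorts 1 and 2) opens Cohort 2 only if Cohort 1 shows no safety signal and its subjects have not reached the organ dose limits.

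**The concern.** Cohort 2 has the same peptide mass as Cohort 1 and a higher activity. A rule that requires excess toxicity in Cohort 1 before opening Cohort 2 works against its purpose: the more toxic 6 GBq is, the more likely the rule is to allow 7.4 GBq. The other two rows fail differently. DRB-B prescribes two actions for one outcome, and DRB-A has no criterion for the cohort it asks about.

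Table 9 is where the SAP states these thresholds before the meetings take place. If the table is wrong, the escalation decisions cannot be checked against a stated rule, and the documented threshold for the optional 300 µg, 7.4 GBq cohort is the reverse of the one the protocol approved.

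**Working it through.** **Count behind 33%.** SAP 3.2.19 glosses above 33% as more than 1 of three to five subjects; SAP 3.2.18 glosses it as more than 2 of 6. Reading 33% as one third, the smallest qualifying count is 2 for n = 3, 4 and 5, and 3 for n = 6, which reproduces both glosses. A literal 0.33 would let 1 of 3 and 2 of 6 qualify and contradict both. One third is used below.

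**DRB-F.** Doses are from SAP Table 1.

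| Cohort | Peptide (µg) | GBq per cycle | Cumulative GBq |
|---|---|---|---|
| 1 | 300 | 6.0 | 18.0 |
| 2 | 300 | 7.4 | 22.2 |
| 5 | 700 | 7.4 | 22.2 |

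From Cohort 1 to Cohort 2 activity rises by 22.2/18.0 = 7.4/6.0 = 1.233, or 23%, with peptide unchanged. At n = 3 the printed Cohort 1 condition is met by 2 or 3 DLTs and failed by 0 or 1. The text after the table, at the same time point (after the third 6 GBq administration), requires at most 33% for 7.4 GBq and reduces activity above that. DRB-C, which governs the same activity step at 700 µg (Cohort 4 to Cohort 5), says NO above 33%.

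Taking the Cohort 1 condition alone, with three independent subjects and an assumed DLT rate p, the chance of meeting it as printed is P(at least 2 of 3) = 3p²(1−p) + p³:

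| Assumed p | As printed (at least 2) | Sign corrected (at most 1) |
|---|---|---|
| 0.10 | 2.8% | 97.2% |
| 0.20 | 10.4% | 89.6% |
| 1/3 | 25.9% | 74.1% |
| 0.50 | 50.0% | 50.0% |
| 0.60 | 64.8% | 35.2% |

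As printed, the chance of passing rises with toxicity. The rates are illustrative; the error does not depend on them.

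DRB-D and DRB-E also start a cohort above 33%, but they are a different kind of rule. DRB-D reads "If >33% DLTs and <67% DLTs in Cohort 4 and receptor modelling suggests Cohort 7 mass dose safer, then start Cohort 7". Activity stays the same, peptide mass rises from 700 to 1300 µg, DLTs are capped, and the new mass must be judged safer. Relative to Cohort 1, DRB-F has none of these features.

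**DRB-B.** With all DLTs counted on one window:

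| n | Wait (above 1/3, below 67%) | NO (above 65%) | Both |
|---|---|---|---|
| 3 | 2 | 2, 3 | 2 |
| 4 | 2 | 3, 4 | none |
| 5 | 2, 3 | 4, 5 | none |
| 6 | 3, 4 | 4, 5, 6 | 4 |

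2/3 = 4/6 = 66.67%, which is above 65% and below 67%. With three subjects, no total leads to waiting alone. The bands name different windows (Cohort 3 against Cohort 3 Cycle 2), but two subjects with Cycle 2 DLTs always meet both. For an assumed Cycle 2 DLT rate q, P(2 of 3) = 3q²(1−q): 0.7% at 0.05, 2.7% at 0.10, 9.6% at 0.20, 22% at 0.33. If the bands are reused at six subjects, a second collision (2 of 3, then 2 of the next 3) has probability [3q²(1−q)]²: 0.07% at 0.10, 0.9% at 0.20, 4.8% at 0.33.

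**DRB-A.** The question concerns Cohort 6 and the criterion decides Cohort 4. Taken as printed, it also says NO to Cohort 4 at 2 of 3 Cycle 2 DLTs, where DRB-B says wait.

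**Related text.** The Part B stopping list in SAP 3.2.19 departs from SAP 1.3.1.3 and Protocol 6.4.2. It adds a neutrophil stop below 1.0 × 10⁹/L, drops the restriction to related AEs, adds an exception for thrombocytopenia under 4 weeks, drops the treatment-related liver toxicity clause, and puts the end visit at 12 weeks instead of 8.

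**The case against.** The strongest reply is that the printed rules could hardly do harm. Even if DRB-F were applied literally, the text after Table 9 would reduce the activity, and SAP 3.2.18 and Protocol 3.8 would bar the next cohort. The second interim analysis must also confirm whether Cohort 2 opens, safety data from all cohorts are reviewed at each DRB, and the core team decides. DRB-B's own cell holds Cohort 4 until Cohorts 1, 3 and 6 are fully recruited, so neither branch opens it after three subjects and more Cohort 3 data will accrue. The general 33% rule arguably answers DRB-A, and its clash with DRB-B disappears if Cohort 4 is a misprint for Cohort 6.

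Timing also matters. The planned study period ends in November 2022 after two years of follow-up, which puts the last planned end-of-treatment visits near November 2020. SAP 4.1 is dated 09 July 2021, and SAP 3.1.3 limits per-lesion dosimetry in Part B to Cohorts 1, 3 and 6. These decisions may be past.

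All of this lowers the stakes, and it stands. It does not correct the table. An override elsewhere in the section means the SAP contradicts itself, the recruitment hold leaves two actions for one outcome, and DRB-A still has no criterion of its own. A sign lost in PDF conversion cannot be excluded, but less-than signs survive in the same table and at-most signs in the surrounding text. SAP section 5 lists no deliberate change to these rules.

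**Conclusion.** The concern holds; the three rows should be corrected. The Cohort 1 sign in DRB-F and the cohort number in DRB-A are plain errors. The DRB-B overlap follows from arithmetic once above 33% is read as the SAP glosses it.

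The size is the direction of a safety threshold for a step of 23% more activity, one of four possible totals with two actions in DRB-B at n = 3 (one of seven at n = 6, none at n = 4 or 5), and one unanswered question. No probability of harm is claimed. The Cohort 5 direction in DRB-F is an inference: the protocol synopsis lets Cohort 2 wait for experience with 7.4 GBq at 700 µg, which suggests that Cohort 5 should be tolerable, but the sponsor must confirm it. The documents do not say which DRBs had met by July 2021, so the change may correct the record rather than a pending decision. Protocol Appendix 3 and the DRB charter were not available.

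**What to change.** Replace the three rows of SAP Table 9.

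- **DRB-F:** start Cohort 2 only if modelling favours 300 µg, DLTs are at most 33% (no more than 1 of 3 to 5 subjects) in Cohort 1 and at most 33% in Cohort 5, and the organ dose condition is met (limits 1.5 Gy bone marrow, 23 Gy kidney); otherwise do not. The sponsor confirms the Cohort 5 direction. Take the organ dose wording from the protocol synopsis, where subjects have not reached the limits. The clause in Protocol 3.8, SAP 3.2.18 and SAP 3.2.19, read literally, is met when two or three of three subjects did reach them, and needs the same correction.
- **DRB-B:** use counts that do not overlap, on one stated DLT window. For example, 0 or 1 of 3 starts Cohort 4, 2 of 3 waits for three more, 3 of 3 is NO. State one action for each total out of 4, 5 and 6.
- **DRB-A:** with DLTs in more than 1 of 3 subjects in Cohort 3 Cycle 2, do not start Cohort 6 Cycle 2 at 1,300 µg.

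Replace the stopping list and end-visit timing in 3.2.19 with a cross-reference to SAP 1.3.1.3 and Protocol 6.4.2. Check Table 12 in Protocol Appendix 3 and the DRB charter for the same text. If the meetings have already taken place, record which rule was applied.

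The cost is a wording correction and a document check; no patients, visits or procedures are added.
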